Infusion of the study drug will be stopped if the mean blood pressure decreases < 35 mmHg and by > 20 mmHg (from pre-study drug mean blood pressure) after initiation of study drug and remains low for 2 hours despite treatment with > 40 ml/kg/24h of fluids and vasoactive medications (with a vasoactive inotrope score of > 30). Once the study drug is discontinued for improvement in oxygenation or a decrease in systemic blood pressure, it will not be restarted even if the condition leading to discontinuation changes (such as change in oxygenation or blood pressure). However, clinical providers can initiate open-label milrinone at their discretion. Study drug will also be stopped in the presence of renal dysfunction and/or development of a large intracranial (intraventricular with distension of the ventricle or parenchymal) bleed/echodensity.

Primary Outcome:

The primary outcome is the oxygenation response, as determined by change in OI (or OSI if no arterial blood gas is available) at 24h after initiation of study drug. In patients that require ECMO or die prior to completion of 24h from the initiation of the study drug, the last OI (or OSI if no arterial blood gas is available) prior to initiation of ECMO or death will be used for analysis. In patients without an arterial line (or if the line is lost), oxygen saturation index (OSI) will be calculated using a preductal oximeter. (Rawat, Chandrasekharan et al. 2015)

Secondary outcomes:

- (i) Oxygenation response at 24 h after initiation of study drug assigning a minimum OI of 40 or OSI of 20 for subjects that need ECMO or die after initiation of study drug infusion but prior to 24h of study-drug infusion. In this analysis if the patient's OI is 30 (or OSI of 15) and is cannulated for ECMO due to hemodynamic instability, he/she will be assigned an OI of 40 (or OSI of 20). However, if the OI prior to ECMO is 47 (i.e., > 40), the higher number (47) will be used for analysis of this secondary outcome.
- (ii) Oxygenation index at 48 and 72 h after initiation of study drug (or OI/OSI at the time of initiation of ECMO or immediately prior to death, for infants placed on ECMO or died before these time points),

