3.5. POTENTIAL RISKS AND BENEFITS TO SUBJECTS

Infants with CDH represent a high-risk population with mortality ranging from 30 to 40%. Additional risks from the use of IV milrinone include systemic hypotension, intracranial hemorrhage (reported in critically ill neonates with PPHN) and arrhythmias (reported in adults). The anticipated benefit is improvement in oxygenation and reduced need for ECMO.

Systemic hypotension is commonly seen in patients with CDH. In recent studies 80-90% of patients with CDH required treatment with vasoactive medications. (Snoek, Capolupo et al. 2016) Patients will be closely monitored for systemic hypotension due to its association with increased right –to-left shunting and hypoxemia. Study drug will be discontinued in the presence of 'severe' or 'life-threatening' systemic hypotension as outlined in the MOP that cannot be explained by other causes (such as sepsis or pneumothorax) and described below.

- a. Severe hypotension:
 - decrement in mean BP > 20 to 30 mmHg compared to the most recent value during the period prior to study drug or at baseline OR
 - receiving extensive volume therapy (40 to 80 ml/kg during a 24-hour period of the study monitoring period: onset of study drug to 24 hours after discontinuation of study drug) OR
 - escalation of vasoactive inotrope score by 20 to 30 compared to the score at baseline
- b. Life-threatening hypotension:
 - Decrease in mean BP > 30 mmHg compared to the most recent value during the period prior to study drug or at baseline OR
 - receiving volume therapy (> 80 ml/kg during a 24-hour period of the study monitoring period: onset of study drug to 24 hours after discontinuation of study drug) OR
 - escalation of vasoactive inotrope score by > 30 compared to the score at baseline)

(i) Vasoactive inotrope score calculation (vasoactive inotrope score = dopamine dose ($\mu\text{g}/\text{kg}/\text{min}$) + dobutamine dose ($\mu\text{g}/\text{kg}/\text{min}$) + epinephrine dose ($\mu\text{g}/\text{kg}/\text{min} \times 100$) + norepinephrine dose ($\mu\text{g}/\text{kg}/\text{min} \times 100$) + phenylephrine dose ($\mu\text{g}/\text{kg}/\text{min} \times 100$) + vasopressin dose ($\text{U}/\text{kg}/\text{min} \times 10000$) (Gaies, Gurney et al. 2010)

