Intracranial hemorrhage has been reported in 2 patients with milrinone use in one case series. Subjects in the study will be closely monitored for intracranial hemorrhage with a first head ultrasound and a repeat ultrasound after completion of the study drug infusion. Study drug is discontinued if a 'severe' or 'life-threatening' intracranial bleed/echodensity as defined in the MOP and as described below.

- a. Severe intracranial bleed: unilateral or bilateral blood/echodensity filling the ventricle(s) resulting in distension without parenchymal bleeding and without a midline shift.
- b. Life-threatening intracranial bleed: Parenchymal hemorrhage/echodensity (including cerebellar hemorrhage) and / or any bleed/ echodensity associated with a midline shift.

Extracranial hemorrhage has not been reported in neonates with PPHN receiving milrinone. However, the study-drug should be discontinued in the presence of 'severe' or 'life-threatening' extracranial bleed (that cannot be attributed to other factors such as trauma, surgery etc,) as outlined in the MOP and described below:

- a. Severe category:
 - pulmonary or GI or other forms of extracranial bleed requiring $>15-30$ ml/kg PRBC transfusion during the study monitoring period: (onset of study drug to 24 hours after discontinuation of study drug) OR
 - associated with a 5 to 10 mm Hg decrease in mean blood pressure from the time prior to the onset of bleeding
- b. Life-threatening category: pulmonary or GI or other forms of extracranial bleed requiring PRBC transfusions (total volume of PRBC > 30 ml/kg during the study monitoring period: onset of study drug to 24 hours after discontinuation of study drug) OR associated with > 10 mm Hg decrease in mean blood pressure from the time prior to onset of bleeding.

Milrinone does not directly induce renal dysfunction. However, renal dysfunction can prolong the half-life of milrinone. New-onset renal dysfunction of 'severe' or 'life-threatening' category as outlined in the MOP) are indications for discontinuation of study-drug.

- a. Severe renal dysfunction: Serum creatinine $> 2 \text{ mg/dL}$ but $\leq 3 \text{ mg/dL}$ OR increase by 0.5 to 1 mg/dL from the most recent value during the period prior to study drug or at baseline
- b. Life-threatening renal dysfunction: Serum creatinine $> 3 \text{ mg/dL}$ OR increase by $> 1 \text{ mg/dL}$ compared to the most recent value during the period prior to study drug or at baseline

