- (ii) Diagnosed with severe or life-threatening renal dysfunction as defined in the MOP
- (iii) Diagnosed with severe or life-threatening arrhythmia as defined in the MOP not attributed to other causes such as electrolyte disturbances or a central line in the right atrium
- (iv) Diagnosed with severe or life-threatening intracranial bleed as defined in the MOP
- (v) Confirmed trisomy 13 or 18 by chromosomal analysis

Note: Respiratory deterioration is common in the natural history of CDH and should not be a reason for discontinuing study drug.

Duration of study intervention

In the absence of complications:

- (i) Milrinone/placebo is continued until oxygenation improves and two OIs obtained at least one hour apart are less than 7 (OSI < 3.5, if no arterial blood gas is available), then weaned according to the protocol below, or
- (ii) Milrinone/placebo is weaned and discontinued after a maximum of 3 days of therapy (72 hours from the initiation).

Surgery and ECMO:

- (i) Milrinone/placebo should preferably be continued if the patient requires ECMO irrespective of the mode of ECMO – VA vs. VV (Reason: although pharmacokinetics and volume of distribution are altered, milrinone may be beneficial with improved cardiac function especially during VV ECMO). (Note: ECMO use varies from center to center, but averages around 30%. This will mean that a fair number of the high risk patients are excluded unless they are enrolled soon after birth)
- (ii) It is recommended that the study drug be continued through surgery. If the surgical team prefers to discontinue the study drug, this indication should be recorded and study drug weaned as per protocol.

(iii) Note: if the clinical team decides to wean the baby off the study drug prior to ECMO or surgery, these reasons are documented as indications for discontinuing the study drug. It is not considered a protocol deviation or violation to wean the medication prior to surgery or ECMO. If serious, potentially drug-related complications occur, drug should be discontinued immediately (without weaning).

Study drug discontinuation criteria:

Milrinone/placebo is discontinued (without weaning) if the patient develops 'severe' or 'life-threatening' hypotension, intracranial or extracranial hemorrhage, renal dysfunction or arrhythmia that cannot be attributed to other causes.

Note:

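### The discontinuation criterion in section 4.2.5 puts one test of cause after five toxicities and cannot be reconciled with section 3.5 for at least two of them

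*Combined protocol and SAP*

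**What the plan says.** The sentence under Study drug discontinuation criteria in section 4.2.5 covers five toxicities of severe or life-threatening grade. It names hypotension first and ends with "intracranial or extracranial hemorrhage, renal dysfunction or arrhythmia that cannot be attributed to other causes". One clause about cause closes the whole list.

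Section 3.5 takes the same five one at a time:

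- **Hypotension:** stop if the event is one "that cannot be explained by other causes (such as sepsis or pneumothorax").
- **Intracranial bleed:** "Study drug is discontinued if a 'severe' or 'life-threatening' intracranial bleed/echodensity as defined in the MOP". There is no test of cause.
- **Extracranial bleed:** stop for an event "that cannot be attributed to other factors such as trauma, surgery etc".
- **Renal dysfunction:** new-onset events of either grade "are indications for discontinuation of study-drug". There is no test of cause. The reason given is: "Milrinone does not directly induce renal dysfunction. However, renal dysfunction can prolong the half-life of milrinone".
- **Arrhythmia:** stop once other causes, such as electrolyte disturbance or central line position, have been ruled out.

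The list under Management of the patient in section 4.2.5 has no test of cause for intracranial bleed (item i) or renal dysfunction (item ii) and has one for arrhythmia (item iii). Item (iv) repeats intracranial bleed. Hypotension and extracranial bleed are absent. The list sends the reader to the text below it for how to discontinue.

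The synopsis (Study Intervention/Methods) also has no test of cause: "Study drug will also be stopped in the presence of renal dysfunction and/or development of a large intracranial" bleed. Item (ii) under Weaning of study drug stops abruptly for all five toxicities and does not mention cause.

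**The concern.** This is the rule that a bedside team applies to an individual infant, and care otherwise follows each center's own practice. If the closing clause is read across the list, an infant with renal dysfunction or an intracranial bleed that has another explanation falls outside the criterion, although section 3.5 calls for a stop.

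Renal dysfunction is the clearest case. Section 3.5 does not regard milrinone as a direct cause; its worry is slower elimination. That worry is the same whether the kidney injury comes from tubular necrosis, sepsis or anything else. A test that excuses events with another cause could therefore excuse most of the infants the rule is meant to protect. The entry criteria in section 4.1.2 take the same view as section 3.5, since they list acute tubular necrosis among the conditions behind disqualifying renal dysfunction.

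A stop is permanent for study drug (Criteria for re-initiation, section 4.2.5), though open-label milrinone may follow. Whether it is required should not depend on which paragraph a site reads.

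**Working it through.** No sample-size, power or error-rate figure is involved. The check compares the two sections toxicity by toxicity, for each span that a clause at the end of the list can cover.

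**Inputs.** The order in the section 4.2.5 criterion is hypotension, intracranial bleed, extracranial bleed, renal dysfunction, arrhythmia. In that order, with T for a test of cause and N for none, section 3.5 reads T, N, T, N, T.

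**Enumeration.** A mismatch is a toxicity where one section has a test of cause and the other does not.

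| Clause covers | Pattern in 4.2.5 | Mismatches with 3.5 | Count |
|---|---|---|---|
| Arrhythmia only | N N N N T | hypotension, extracranial | 2 |
| Last two | N N N T T | hypotension, extracranial, renal | 3 |
| Last three | N N T T T | hypotension, renal | 2 |
| Last four | N T T T T | hypotension, intracranial, renal | 3 |
| All five | T T T T T | intracranial, renal | 2 |

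The minimum is 2 of 5. Full agreement would need the clause to attach to hypotension, extracranial bleed and arrhythmia while skipping the two items between them, which the sentence does not allow.

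The first and last rows are the readings a clinician would plausibly adopt, and they err in opposite directions. The whole-list reading adds a test for two toxicities that have none in section 3.5. The arrhythmia-only reading drops the exemption that section 3.5 gives to hypotension and extracranial bleed.

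**Worked case.** An infant on study drug develops acute tubular necrosis with creatinine 2.8 mg/dL. Section 3.5 grades this severe (above 2 and up to 3 mg/dL).

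- Section 3.5: stop.
- Management list, item (ii): stop.
- Synopsis: stop.
- Weaning item (ii): stop, abruptly.
- Discontinuation criterion, whole-list reading: not triggered, because another cause is known.

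The one statement that fails to call for the stop is the one headed as the discontinuation criterion.

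**The case against.** The strongest reply is that nothing is contradicted in the strict sense. Each statement says to stop if a condition holds, and none says to continue otherwise. In the worked case a site that follows every statement stops the drug, and the Note after the criterion lets the clinical team stop at any time. This stands. A reader might infer that the criterion removes renal and intracranial stops from the protocol; the documents do not support that.

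A second reply is that the clause governs the manner of stopping and not whether to stop, since the sentence concerns discontinuation without weaning and the text just above it speaks of potentially drug-related complications. That would remove the disagreement with section 3.5 for intracranial bleed and renal dysfunction. But the sentence stands under a heading about discontinuation criteria, and Weaning item (ii) makes the stop abrupt for all five toxicities without asking about cause. The reading moves the inconsistency without resolving it.

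A reader might also infer that the hypotension rules collide, because the synopsis says "Infusion of the study drug will be stopped if the mean blood pressure decreases < 35 mmHg and by > 20 mmHg" with no test of cause while section 3.5 exempts causes such as sepsis. The thresholds differ. The synopsis needs all its conditions together: mean pressure below 35 mmHg, a fall of more than 20 mmHg, and 2 hours' persistence despite more than 40 ml/kg/24h of fluid and a vasoactive inotrope score above 30. Any one of the section 3.5 criteria is enough for its stop. A stop for refractory hypotension whatever the cause can coexist with a milder stop that asks about cause.

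Nor should the absence of a qualifier in the synopsis, the Figure 6 legend or the weaning text be counted as a separate rule against a test of cause. Short forms often leave qualifiers out.

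The manual of operations (MOP) is not among the documents. Section 3.5 cites it for severity grading, so it is not shown either to settle the question of cause or to leave it open.

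**Conclusion.** The criterion in section 4.2.5 is wrong as written. Its single clause disagrees with section 3.5 on 2 or 3 of the 5 toxicities, depending on scope, and never on fewer than 2. On the whole-list reading it adds a test of cause for intracranial bleed and renal dysfunction, and for renal dysfunction that defeats the stated half-life rationale.

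The practical reach is small. Only events with another identified cause are affected, and the documents give no rate for them. The exposure is a site that relies on this sentence alone. The conclusion takes section 3.5 as the sponsor's intent, because it treats each toxicity separately and gives the renal rationale. No effect on power or type I error follows. Severity: minor.

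**What to change.** Reword the criterion along these lines: *Study drug is discontinued without weaning (a) for severe or life-threatening intracranial bleed or new-onset renal dysfunction, regardless of cause, and (b) for severe or life-threatening hypotension, extracranial bleed or arrhythmia not attributable to another cause.*

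In the Management of the patient list, replace the duplicate item (iv) with extracranial bleed not attributed to another cause, and add hypotension on the terms of section 3.5.

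Keep the synopsis stop for refractory hypotension, with all its conditions required jointly, as a separate backstop that does not depend on cause. Keep the clinical team's discretionary stop. Do not redirect the synopsis, the Figure 6 legend or Weaning item (ii) to the reworded criterion as a tidying step. That would put a test of cause on hypotension, extracranial bleed and arrhythmia wherever those texts now stop without one, and would need its own decision.

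The cost is protocol wording, a matching check of the MOP, and possibly a few more mandatory stops for intracranial bleed or renal dysfunction with another cause.

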3.2. SECONDARY OUTCOMES

- (i) Oxygenation response at 24 h after initiation of study drug assigning a minimum OI of 40 or OSI of 20 (if no arterial blood gas is available) for subjects that need ECMO or die after initiation of study drug infusion but prior to 24h of study-drug infusion. In this analysis if the patient's OI is 30 (or OSI of 15) and is cannulated for ECMO due to hemodynamic instability, he/she will be assigned an OI of 40 (or OSI of 20). However, if the OI prior to ECMO is 47 (i.e., > 40), the higher number (47) will be used for analysis of this secondary outcome.
- (ii) Oxygenation index at 48 and 72 h after initiation of study drug (or OI/OSI at the time of initiation of ECMO or immediately prior to death, for infants placed on ECMO or died before these time points),
- (iii) Change in echocardiographic findings – velocity of tricuspid regurgitation, left ventricular ejection fraction, position of the interventricular septum and direction of shunt at the PDA and PFO level – prior to and 24-72h after starting the study

medication. This outcome will be available only for those infants who have a pre-study drug echocardiogram and a second echocardiogram between 24-72 h after initiation of study drug. These data will be extracted from echocardiograms performed for clinical indications.

- (iv) Vasoactive Inotrope score and systemic blood pressure
- (v) Area under the curve for inspired oxygen after initiation of the study drug over the first 72 hours of study-drug infusion (or prior to ECMO or death, whichever is earlier) (Note: inspired oxygen and ventilator data from 4 time points per day – every 6 hours will be recorded to calculate area under the curve),
- (vi) If subsequent to the study drug, any additional inotrope or pulmonary vasodilator is used (such as iNO), we will evaluate the oxygenation response to these agents. If inotropes or vasodilators were used prior to the initiation of study drug, similar values will be recorded. The OI (or OSI) and $\text{PaO}_2/\text{FiO}_2$ ratio prior to and after initiation of the inotrope / vasodilator are recorded (these data are recorded at 6 hour intervals; the date and time of initiation of individual inotropes and vasodilators is recorded). The change in OI (or OSI) and $\text{PaO}_2/\text{FiO}_2$ ratio in response to these agents is evaluated as a continuous variable and arbitrarily classified into responders, partial responders and non-responders similar to prior trials (1997, 1997).

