 - Midline shift secondary to mass effect from an intracranial hemorrhage
- thrombocytopenia (platelet count < 80,000/mm³) despite blood product administration on the most recent blood draw prior to randomization
- coagulopathy (PT INR > 1.7) despite blood product administration on the most recent blood draw (if checked – there is no reason to check PT for the purpose of this study)
- aneuploidy associated with short life span (such as trisomy 13 or 18) will not be included in the study (infants with trisomy 21 can be included in the study)

- use of milrinone infusion prior to randomization (the use of other inhaled pulmonary vasodilators such as iNO, inhaled epoprosternal, inhaled Treprostinal, inhaled PGE1 and oral such as endothelin receptor antagonists is permitted – Note: it is unlikely to be on oral pulmonary vasodilators early in the course of CDH)
- ongoing therapy with parenteral (intravenous or subcutaneous) pulmonary vasodilators such as IV/SQ prostacyclin analogs (Epoprostenol – Flolan® or Treprostinal – Remodulin®) or IV phosphodiesterase 5 inhibitors (sildenafil – Revatio®) at the time of randomization. Administration of IPGE1 is not an exclusion criteria. In addition, initiation of therapy with these two classes of parenteral medications (except IPGE1) during the first 24 hours of study drug initiation is not permitted and will be considered a protocol deviation. The risk of systemic hypotension is high during the first 24 hours of study-drug (milrinone) infusion and hence parenteral administration of other pulmonary vasodilators is avoided to minimize risk of hypotension.
- Subjects already on ECMO or patients who are being actively considered for ECMO by the neonatal or surgical team
- Infants with hypoxic-ischemic encephalopathy (HIE) undergoing therapeutic hypothermia
- attending (neonatal, critical care or surgical) refusal for participation in the trial (including concern about presence of hemodynamic instability)

Note:

1. A clotting profile evaluation is not required prior to enrollment. However, a cranial ultrasound (covered by the study budget) must be obtained either prior to initiation of study drug or within 4 hours of initiation of study drug. Not obtaining a cranial ultrasound within this time period will be considered a protocol deviation.

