4.2. DETAILED STUDY PROCEDURES

For the purpose of the study, time period prior to study drug is defined as 12 hours prior to initiation to 30 minutes prior to initiation of study drug. Baseline is defined as the period 30 min prior to initiation of study drug. The monitoring period is defined as the period of study drug infusion and the first 24-hours following study drug cessation.

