Criteria for re-initiation of study drug:

After the patient has met criteria for study drug discontinuation once (due to improvement in oxygenation and meeting OI criteria, or due to side effects such as severe hypotension, intracranial bleeding or renal dysfunction), study drug is discontinued and cannot be reinitiated even if the indication for initial discontinuation is resolved (for e.g., OI exceeds 10 after cessation of study drug or hypotension is resolved and blood pressure is normal etc.,). The clinical team may start open-label milrinone.

During the post-study drug infusion period, data regarding open-label milrinone use, pressor use, and vasodilator use will be recorded for 24 hours after cessation of study-drug.

Fluid intake:

- (i) As systemic hypotension and fluid bolus administration are common in patients with CDH and PPHN, it is important to record daily fluid intake.
- (ii) Total fluid intake (including maintenance fluids/TPN, flushes, medications, boluses and blood products) will be recorded for three 24-hour periods as entered in the nursing notes/EMR (please see MOP for details).

Clinical criteria for ECMO:

The decision to place an infant with CDH on ECMO is ***entirely up to the clinical team***. Many centers prefer to use ECMO for preoperative stabilization. The following general guidelines are provided as criteria for ECMO (Reiss, Schaible et al. 2010) (Snoek, Reiss et al. 2016):

- (i) Oxygenation index is consistently ≥ 40 for at least 3 h and/or
- (ii) Inability to maintain preductal saturations $> 85\%$ or postductal saturations $> 70\%$ and/or
- (iii) Increased PaCO_2 and respiratory acidosis with $\text{pH} < 7.15$ despite optimization of ventilator management and/or
- (iv) $\text{PIP} > 28 \text{ cm H}_2\text{O}$ or mean airway pressure $> 17 \text{ cm H}_2\text{O}$ is required to achieve saturations $> 85\%$ and $\text{PaCO}_2 < 65 \text{ mmHg}$ and/or
- (v) Inadequate oxygen delivery with metabolic acidosis as measured by elevated lactate $\geq 5 \text{ mM/L}$ and $\text{pH} < 7.15$ and/or
- (vi) Systemic hypotension (mean blood pressure $< 30 \text{ mmHg}$), resistant to fluid and inotropic support, resulting in hypoperfusion and/or oliguria (urine output $< 0.5 \text{ mL/kg/h}$) for at least 12-24h

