5.4 STATISTICAL ANALYSIS PLAN

Baseline data will be collected prior to randomization including gestational age, side of the diaphragmatic hernia, birth weight, mode of delivery and arterial blood gas parameters (oxygenation index-OI) and/or pulse oximetry data (oxygen saturation index-OSI). Data from a baseline clinical echocardiogram is recorded (if performed prior to study drug initiation or within 2h of initiation of study drug). During the infusion of study drug, arterial blood gas parameters and hemodynamic data (blood pressure, heart rate and echocardiography results) will be recorded. After completing the study infusion, surgical details, and mortality information will be collected. Among survivors, respiratory and nutritional status at discharge and at 4, 8 and 12 months of age will be collected.

Data will be presented as mean \pm SD for normally distributed variables and as median and ranges (with percentiles) for non-normally distributed data. All analysis will be by intention-to-treat. Baseline characteristics will be compared between treatment groups using chi-square and Fisher's exact test for discrete variables and t-test and ANOVA for continuous variables. The primary outcome, difference from baseline OI at 24 h, will be compared between treatment groups using a general linear model adjusted for the stratification factor of HRF severity. Other continuous outcomes will be analyzed similarly. Models for longitudinal outcomes such as oxygenation and vasoactive inotrope scores (short-term) and nutritional and pulmonary outcomes at 12 months (long-term) will include the effect of time, the interaction between time and treatment, and random effects to account for the correlation between measures taken on the same individual over time. Categorical outcomes will be analyzed using analogous generalized linear models. Cox regression models (with adjustment for HRF severity) will be used to plot proportion of responders who survive without ECMO against survival time in hours. Analyses may adjust for clinical site if treatment assignments are severely imbalanced for some sites provided that it is computationally feasible to do so. The potential influence of baseline measures such as time of diagnosis – antenatal vs. postnatal, side of the defect, and gender on pulmonary and nutritional outcome will be explored through the use of additional models similar to those described above.

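### Pressor recording is required only to 24 h after study drug stops, so infants stopped early for response or hypotension have no required vasoactive inotrope score (VIS) at later times

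*Combined protocol and SAP*

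**What the plan says.** Section 3.2 lists outcome (iv) as "Vasoactive Inotrope score and systemic blood pressure", with no time point. Section 5.4 states "All analysis will be by intention-to-treat". The sentence there that begins "Models for longitudinal outcomes such as oxygenation and vasoactive inotrope scores (short-term" goes on to specify time, a time-by-treatment interaction and random effects. Section 4.2.5 defines VIS as a weighted sum of pressor doses, so it cannot be computed without dose records.

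Under the re-initiation criteria in section 4.2.5, "pressor use, and vasodilator use will be recorded for 24 hours after cessation of study-drug". Section 4.2 uses the same window: "The monitoring period is defined as the period of study drug infusion and the first 24-hours following study drug cessation". Section 5.4 describes blood pressure, the other half of outcome (iv), in a sentence that opens "During the infusion of study drug, arterial blood gas parameters and hemodynamic data".

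Under section 4.2.5 the drug stops after two OIs below 7 at least an hour apart, or at once for severe or life-threatening hypotension, and cannot be restarted. One criterion for severe hypotension in section 3.5 is "escalation of vasoactive inotrope score by 20 to 30 compared to the score at baseline". Section 4.1.2 adds: "The risk of systemic hypotension is high during the first 24 hours of study-drug (milrinone) infusion".

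**The concern.** Recording is tied to the end of treatment rather than to time from initiation, and the end of treatment depends on what happens to the infant. A VIS rise can itself trigger the stop that starts the 24 h countdown on VIS recording. Oxygenation is treated differently: section 3.2 fixes OI at 48 and 72 h after initiation and the inspired-oxygen area under the curve over 72 h.

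If milrinone does what the trial hopes (lowers OI) or fears (lowers blood pressure), follow-up for VIS is shorter in the milrinone arm. Later time points in the longitudinal model would then rest on infants still on drug or recently off it, and the time-by-treatment contrast need not be the intention-to-treat difference. Safety is specific aim 2, and section 5.5.3.2 says the pilot will inform a 752-infant trial, so the later haemodynamic course is worth recording without selection.

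**Working it through.** **1. Recording window.** If drug stops at hour s, required recording ends at s + 24.
- Missing time before 48 h: 48 − (s + 24) = 24 − s, when s < 24.
- Missing time before 72 h: 72 − (s + 24) = 48 − s, when s < 48.
- Examples: a stop at 12 h gives VIS to 36 h; at 24 h, to 48 h; at 36 h, to 60 h; at 48 h, to 72 h.

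Every infant is covered to 24 h, barring death.

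**2. The plan's design inputs (section 5.1).** 33 per arm, difference in OI change 4.6, SD of change 6.2, two-sided alpha 0.05. The noncentrality is 4.6 / (6.2 × √(2/33)) = 3.01, which with 64 df gives power 84.3%. The stated 84% reproduces. The plan gives no figure for VIS.

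**3. How many infants might stop for response.** A simple indicator is one OI below 7 at 24 h among infants who meet OI ≥ 10 at entry. Baseline OI is taken as lognormal, truncated at 10. OI at 24 h is baseline plus a normal change with SD 6.2 and mean 0 (placebo) or −4.6 (milrinone). Three baselines can be built from the documents:

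| Baseline before truncation | Source | Milrinone, OI < 7 | Placebo, OI < 7 |
|---|---|---|---|
| 10.6, SD 5.6 | case series, section 5.1 | 34% (11 of 33) | 14% (5 of 33) |
| 20, SD 8 | Table 6, OI ≥ 10, survived without ECMO | 17% (6 of 33) | 6% (2 of 33) |
| 29.5, SD 17.4 | Table 6, OI ≥ 10, both outcome groups pooled | 9% (3 of 33) | 3% (1 of 33) |

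Pooled mean: (21 × 20 + 36 × 35) / 57 = 29.5. Pooled SD: √{[20 × 8² + 35 × 19² + 21 × (20 − 29.5)² + 36 × (35 − 29.5)²] / 56} = 17.4.

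The range is therefore 3 to 11 milrinone infants against 1 to 5 placebo infants. Requiring two low values lowers these counts. Stops between 24 and 48 h, and hypotension stops, raise them.

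**4. Effect on the planned model.** This needs VIS values, which the documents do not give. One simulation used 4,000 infants per arm, 12-hourly values, and a model with categorical time by arm and a random intercept. Assumptions: baseline OI 20, SD 8, truncated at 10; VIS mean 15, between-infant SD 7, residual SD 5; 0.5 VIS points per OI point. The 72 h difference (milrinone minus placebo) was:
- No on-drug pressor rise and no hypotension stops: −2.44 on all data, −2.33 on recorded data; shift +0.11.
- A 5-point on-drug rise and hypotension stops of 20% versus 5%: 1.35 on all data, 4.09 on recorded data; shift 4.09 − 1.35 = +2.74, against a full-data standard error of 2.43 with 33 per arm.

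The second result rests on assumed rates and shows only that the shift need not be zero.

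**The case against.** The strongest reply is that the plan sets no 48 h or 72 h VIS time point. Section 5.4 says only short-term, and the first 24 h, where section 4.1.2 places the high hypotension risk, are fully recorded. The hypotension that causes a stop is also captured as an adverse event over infusion plus 24 h, so VIS is not the only haemodynamic safety measure, nor shown to be the main one. Random effects give some protection when missingness depends on VIS already observed. The manual of procedures is not available here, and section 4.2.5 does not forbid longer recording.

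Much of this stands, and it limits the point to later VIS values. It does not remove it: a longitudinal model with a time-by-treatment term needs a common time span, the stated recording rule does not provide one, and OI, which drives response stops, is not named as a covariate in that model.

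A reader might infer much larger losses from the plan's means. Taking 6.0 and 10.6 as arm means with SD 6.2 gives Φ((7 − 6.0)/6.2) = 56% and Φ((7 − 10.6)/6.2) = 28% below 7, about 19 and 9 of 33. The documents do not support that. Three of the five infants with OI data in Table 5 start below 10 and would be ineligible. A lognormal with mean 10.6 and SD 5.6 puts 55% of infants below the entry threshold and 28% already below 7.

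Recording longer also raises two complications. Section 4.2.5 leaves milrinone out of the VIS because infants are not on open-label drug during the study infusion, which no longer holds after a stop. Section 5.1 expects about 40% ECMO or death, so some later values would fall on ECMO.

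**Conclusion.** The point holds as a modest design weakness in a secondary outcome. As written, the plan lets the required VIS follow-up end according to response or hypotension, and no other section extends dose recording to a fixed time from initiation. Outcome (vi) records when inotropes start but does not mention doses.

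Unequal loss by arm is a conditional expectation, not a stated fact. It follows if milrinone lowers OI or causes hypotension, and the counts of 3 to 11 versus 1 to 5 of 33 are illustrative: they depend on baseline OI, use one OI rather than two, and omit hypotension stops.

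A reader might go further and conclude that the planned model will be biased against milrinone by a known amount. The documents do not support this. The shift is near zero with no on-drug pressor rise and no unequal hypotension stops, and otherwise its size is unknown. The primary outcome, sample size and stopping rules are not affected.

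**What to change.** In section 4.2.5, require pressor doses, blood pressure and open-label milrinone use to be recorded in every infant to the later of 72 h after initiation or 24 h after cessation, whether or not study drug is still running.

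In section 5.4:
- State that VIS and blood pressure are compared at 24, 48 and 72 h after initiation in all randomized infants.
- Keep the VIS formula without milrinone, and report open-label milrinone by arm.
- State how values on ECMO or after death are handled, for example as already done for OI, with the last value before either event.

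The cost is a few sentences and at most 48 − s further hours of abstraction for an infant stopped at hour s < 48 (36 h for a stop at 12 h). Section 4.2.5 already takes fluid intake for three 24-hour periods from the nursing notes or electronic record. Dosing and the adverse-event window stay as they are.
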